8.1.1 Definitions of Adverse Event Terms

Study Product: For this protocol, the term "study product" is synonymous with IP

Date of Onset: The date that the signs and symptoms or diagnosis of the AE began

Severity: Severity will be assessed for each AE and defined using

the following criteria:

Mild – Is a transient discomfort and does not interfere in a significant manner with the subject's normal functioning level. The AE resolves spontaneously or may require minimal therapeutic intervention.

Moderate – Produces limited impairment of function and can require therapeutic intervention, but produces no sequelae.

Severe – Results in a marked impairment of function and can lead to temporary inability to resume usual life pattern. The AE produces sequelae requiring (prolonged) therapeutic intervention.

Causality: Causality Assessment – A determination is made by the Investigator

and sponsor as to whether there is a reasonable possibility that the device or drug is etiologically related to/associated with the AE.

Causality assessment includes, for example, assessment of temporal relationships, association (or lack of association) with underlying disease, treatment association (or lack of association), presence (or absence) of a more likely cause, and physiologic plausibility. Categories for causality assessment are "related," "possibly related," "unlikely related" and "not related."

Related: An AE follows a strong temporal relationship to the device or drug, and another etiology is unlikely or significantly less likely.

Possibly Related: An AE follows a reasonable temporal relationship to the device or drug, and an alternative etiology is equally or less likely compared to the potential relationship to the device or drug.

Unlikely Related: An AE has little or no temporal relationship to the device or drug and/or a more likely alternative etiology exists.

Not Related: An AE that is due to underlying or concurrent illness, complications, concurrent treatments or effect of another concurrent drug/therapy and is not associated to the device or drug (i.e. does not follow a reasonable temporal relationship to the use of the device or drug, or has a much more likely alternative etiology).

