The process for the collection of subject reported events will be the same for both Evaluable Treatment periods. Raw events will be collected through the Weekly Assessments, as well as routine medical record review and standard of care communications with the subject and/or care partner.

All AEs and SAEs, regardless of relatedness, should be recorded.

Additionally, any AE voluntarily reported by the subject should be recorded and verified by the Investigator or designee on the appropriate source documents and eCRF pages.

The outcome/resolution of all AEs and SAEs will be determined by the Investigator and documented on the AE eCRF. Investigators will be instructed to follow all AEs/SAEs as follows: Unrelated AEs will be followed until resolution or until the end of the study whichever occurs first. Adverse device effects (related AEs) and all SAEs (related or not) will be followed until resolution or stable, including following the subject after the end of the study if necessary. The outcome categories that can be chosen on the eCRF by the Investigator include: Fatal, not recovered/not resolved (this outcome is reached for AEs which are ongoing when the subject's end of study is due to death related to another AE), Recovering/Resolving (this outcome is reached for AEs which are ongoing at the subject's end of study), Recovered/Resolved with Sequelae (if there are some residual effects caused by the event), Recovered/Resolved, and Unknown.

All SAEs regardless of their relationship to the study product will be submitted to Sponsor or designee by the Investigator or designee within 24 hours of becoming aware of the event. If an investigator becomes aware after study completion of an SAE that occurred in a subject during their participation in the study, the SAE must be reported on the SAE Form within 24 hours after awareness. Serious adverse events occurring within 30 days of study completion (per subject) will also be reported.

An AE can result from the use of the study product in accordance with the protocol, as well as from an accidental or intentional misuse of the study product or any other treatment error such as unintentional administration or use of another product during the course of the study.

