8.2 Adverse Event Reporting

8.2.1 Reporting Adverse Events to Sponsor/Designee

During the course of the study, the Investigator or designee will routinely monitor each subject for the occurrence of any AE/ADE. If an AE/ADE occurs, the Investigator or designee will complete the AE eCRF which includes the following:

- Description of the event
- Start and stop date of the event
- Timing of the event (prior to first study treatment, during treatment set-up, during treatment, within 4 hours after treatment ends, > 4 hours after treatment ends)

[figure not shown]

- Seriousness of the event (yes, no) (assessed by PI or Sub-I)
- Severity of the event (mild, moderate, or severe) (assessed by PI or Sub-I)
- Causality of the event (related to treatment and/or related to the device) (assessed by PI or Sub-I)
- Action taken
- Outcome of the event (fatal, not recovered/not resolved, recovered/resolved with sequelae, recovered/resolved, and unknown)

All SAEs must be reported to the Sponsor/designee within 24 hours of the Investigator or designee becoming aware of its occurrence. The informed site team member should also contact their site monitor by phone or email to notify him/her of the event. This requirement is irrespective of whether the AE is thought to be possibly related to the study product or not. Expedited Reporting of Serious Adverse Events and Suspected Unexpected Serious Adverse Reaction (SUSAR). Sponsor/designee will assess each SAE reported by the Investigator to determine if the SAE qualifies as an expedited report according to FDA criteria. Sponsor/designee will report to FDA according to the applicable time requirements.

Per regulations, when an Unexpected Adverse Device Effect (UADE) or SUSAR occurs Investigators will receive a letter from Sponsor/designee describing the UADE/SUSAR. The Investigator should file this letter within their Investigator Study Binder. Additionally, the expedited report letter should be submitted by the Investigator to their IRB/REB, as appropriate per FDA regulations.

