9.5 Secondary Endpoints

 Adverse events will be mapped to a primary MedDRA System Organ Class (SOC) and Preferred Term (PT). Anticipated AEs and SAEs and unanticipated AEs and SAEs will be summarized during each Evaluable Period by SOC and PT. In addition, all devicerelated AEs and SAEs will be summarized during each Evaluable Period by SOC and PT.

An overview of the total number of AEs and SAEs (anticipated, unanticipated, and device-related) during each Evaluable Period will be provided. In addition, for each Evaluable Period an overview will be provided of the total number of subjects having at least 1:

- Anticipated AE
- Anticipated SAE
- Unanticipated AE
- Unanticipated SAE
- Device-related AE
- Device-related SAE

The proportion of subjects having at least one AE within each of these six AE subgroups will be compared between Evaluable Periods with exact McNemar's tests. For each of these six AE subgroups the hypotheses will be:

$$H_0: P_u = P_a$$

 $H_a: P_u \neq P_a$

Where P_u = Proportion of subject having at least 1 event during unassisted treatments and P_a is the proportion of subjects having at least 1 event during the Assisted treatments.

Identifying the number of subjects who had at least 1 event during assisted treatment and no event during unassisted treatment as n_{12} , and subjects who have no event during assisted treatment and at least 1 event during unassisted treatment as n_{21} , the indicator

$$Q = \frac{(n_{12} - n_{21})^2}{(n_{12} + n_{21})}$$
 will be compared to x^2 with 1 Degree of Freedom if

$$(n_{12} + n_{21}) > 20$$
. Otherwise the correction $Q = \frac{(|n_{12} - n_{21}| - 1)^2}{(n_{12} + n_{21})}$ will

be used. The Null Hypothesis will be rejected if the P-value for the x^2 is less than 0.10.

No multiplicity adjustment will be done for these secondary endpoints.

Furthermore, the proportion of subjects having AEs within each of these six AE subgroups will be summarized by SOC, PT and severity (mild, moderate or severe) during each Evaluable Period for the most severe rating of each AE per subject.

 The incidence of decreased serum phosphorus defined as at least 1 post-dialysis serum phosphorus level < 2.2 mg/dL, the incidence of elevated serum phosphorous defined as a least 1 post-dialysis serum phosphorus level > 5.5 mg/dL, will each be compared between Evaluable Periods with exact McNemar's tests.

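### The AE severity scale in 8.1.1 mixes functional impairment with sequelae, so two kinds of event fit no grade and the by-severity tables in 9.5 are unreliable

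*Combined protocol and SAP*

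**What the plan says.** Section 8.1.1 gives three severity grades.

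- Mild: "Is a transient discomfort and does not interfere in a significant manner with the subject's normal functioning level". It resolves by itself or with minimal intervention.
- The middle grade, Moderate, is worded "Produces limited impairment of function and can require therapeutic intervention, but produces no sequelae".
- The top grade, Severe, opens with "Results in a marked impairment of function and can lead to temporary inability to resume usual life pattern". Its next sentence reads "The AE produces sequelae requiring (prolonged) therapeutic intervention".

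Section 8.2.1 offers the same three grades on the AE eCRF, assigned by the principal investigator or a sub-investigator. Sequelae are also recorded in a separate outcome field. Section 8 lists its categories, among them "Recovered/Resolved with Sequelae (if there are some residual effects caused by the event), Recovered/Resolved, and Unknown", and 8.2.1 repeats the field.

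Section 9.5 states that the proportions of subjects with AEs in six subgroups (anticipated, unanticipated and device-related AEs and SAEs) "will be summarized by SOC, PT and severity (mild, moderate or severe") for each Evaluable Period, taking the worst rating of each AE per subject.

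**The concern.** A severity grade should say how intense an event was. This scale also asks what the event left behind, which is a matter of outcome. The two need not go together. Section 8.1.7 and Appendix 1 list reactions such as hypotension with fainting, seizures and air embolism, any of which can be intense and then pass without residue. If the definitions are applied as written, the site has no correct box for such an event.

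What is at stake is the reading of the severity tables. Up to 10 sites will grade AEs. If some choose Moderate because the subject recovered and others choose Severe because impairment was marked, the same event appears in different rows depending on where it was graded.

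**Working it through.** The protocol gives no figure to reproduce and no arithmetic applies. The check is to cross the two attributes that the definitions use.

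**Step 1. What each grade requires, from 8.1.1.**

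- Mild: no significant interference with function. Sequelae are not mentioned, but the event is transient.
- Moderate: limited impairment and no sequelae.
- Severe: marked impairment and sequelae. The sequelae sentence is a flat statement. It is not softened by *can* or *may*, and no *or* joins it to the impairment sentence.

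**Step 2. Cross-classification of the upper two levels of impairment.**

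| Impairment | No sequelae | Sequelae |
|---|---|---|
| Limited | Moderate | no grade |
| Marked | no grade | Severe |

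Marked impairment with full recovery fails Severe on sequelae, fails Moderate because impairment is not limited, and fails Mild because function is disturbed. Limited impairment with sequelae is shut out of Moderate by its last clause and out of Severe by the degree of impairment. Two of the four cells are therefore undefined.

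**Step 3. Internal consistency of Severe.** Its first sentence speaks of an inability that may be only temporary, which suggests that recoverable events belong there. Its second sentence requires sequelae. The two point in different directions.

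**Step 4. Is the gap closed elsewhere?** Section 8.2.1 provides no fourth grade. Neither section 8 nor section 9.5 tells the site to grade on the worst single element. The outcome field records sequelae but does not alter the severity grade.

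**Step 5. Which analyses use the grade?**

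| Analysis | Uses severity? |
|---|---|
| Primary AE rate ratio (9.4.1), response is the total AE count | No |
| McNemar comparisons of the six AE subgroups (9.5) | No |
| SAE status (8.1.2), judged on its own criteria | No |
| Summary by SOC, PT and severity per period (9.5) | Yes |

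Only the last row is exposed. Because that summary covers the SAE subgroups too, the severity split within SAEs is open to the same ambiguity, although the SAE counts are not.

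**The case against.** The strongest reply is that the consequence is small, and most of that reply stands.

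- The most dangerous events are captured by other means. Section 8.1.2 judges seriousness without reference to severity, and its important-medical-event category gives as examples convulsions and allergic bronchospasm treated intensively without hospitalization. Full recovery does not remove SAE status. What remains exposed is mainly intense, reversible AEs that are not serious, plus the severity label on those that are.
- An investigator grading by best fit could still choose Severe, since Moderate is confined to limited impairment. This is fair. Moderate is the only grade that expressly says no sequelae, so the wording pulls a resolved event towards it, but that under-grading is the likelier error is an inference.
- Sequelae may be unknown when the AE is first entered, but AEs are followed (section 8) and entered data can be changed under an audit trail (10.1). Timing alone is not a fault.

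Two stronger readings are tempting. A reader might infer that the scale understates harm in the Unassisted Home Evaluable Period, because 7.1.4 has AEs collected at treatment and 7.1.7 through the weekly call, by which time an acute event may have passed. The documents do not support that as a finding: one scale applies to both periods, and section 8 states that subject-reported events are collected by the same process in both. A reader might also infer that the clinical determination of safety in 9.2 is undermined, since it rests on the rate and type of AEs. Section 9.2 explains type as device-relatedness, and neither rate nor device-relatedness depends on the severity grade.

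None of these replies supplies a grade for the two empty cells.

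**Conclusion.** The point holds in a limited form. Taken as written, the definitions leave two of four combinations of impairment and sequelae without a grade, and Severe is in tension with itself. This is a stated rule that fails when followed, not a missing detail. The consequence is that the descriptive by-severity tables in 9.5 may mix events graded on different principles and cannot be relied on.

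The conclusion assumes that the sentences within each definition apply together, which is the plain reading but not the only one a site might adopt. The documents do not show how investigators would resolve the gap, the net direction of misgrading, or any difference between periods. The number of events affected cannot be derived. The primary safety result, the McNemar comparisons and the SAE classification stand as they are.

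**What to change.** In 8.1.1, grade severity on impairment of function alone. Delete the closing no-sequelae clause from Moderate and the sentence "The AE produces sequelae requiring (prolonged) therapeutic intervention" from Severe. The scale then runs from no significant interference (Mild) through limited impairment (Moderate) to marked impairment (Severe), with no empty cell. Leave sequelae to the outcome field already provided in section 8 and 8.2.1, so no information is lost. Add a line to the eCRF completion guidance saying that severity is graded on function and does not depend on recovery.

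The cost is an edit to two definitions and that guidance. No endpoint, sample size or analysis model changes. There are two drawbacks. More AEs may be graded severe than under the present wording. And if AEs have already been entered, all of them, in both Evaluable Periods, must be rechecked under the new definition. Every subject goes through the Assisted period before the Unassisted one, so a partial regrade, or a change applied only from a given date, would confound the grading rule with period and create a bias that the documents do not show at present.

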8.1.2 Serious Adverse Events

The following criteria qualify an AE as an SAE:

Death: An event resulting in death (including a fetal death).

Life-threatening: In the opinion of the Investigator, an event that would have resulted

> in immediate death if medical intervention had not been undertaken. This does not include an event that would have been

fatal if it had occurred in a more severe form.

An event resulting in inpatient admission of the subject to the Hospitalization:

> hospital. (Note: Inpatient hospitalization refers to any inpatient admission, regardless of length of stay). Visits to the emergency room or outpatient facility do not constitute hospitalization for the

purpose of the definition.

Prolongation of

An event that prolongs the subject's stay in the hospital. By Hospitalization: definition, this is a different event from the event that resulted in

the hospitalization.

Congenital

An abnormality detected at or after birth in the offspring of a study Abnormality:

subject.

Persistent or

Significant

Disability/Incapacity:

An event that substantially interferes with the subject's daily activities of living. This category is not intended to include events of relatively minor medical significance such as minor trauma,

diarrhea, nausea, etc.

Important Medical

Event:

A medically important event or reaction that may not be immediately life-threatening or result in death or hospitalization, but may jeopardize the subject or requires intervention to prevent one of the other outcomes listed above. Examples of such events include intensive treatment in an emergency room or at home for allergic bronchospasm, blood dyscrasias or convulsions that do not result in hospitalization, or development of drug dependence or drug abuse.

8.1.3 Adverse Drug/Device Reaction

All noxious and unintended responses to a medicinal product that are related to any dose should be considered adverse drug reactions (ADR). The phrase "responses to a medicinal product" means that a causal relationship between a medicinal product and an AE is at least a reasonable possibility (i.e., the relationship cannot be ruled out).

8.1.4 Unexpected Adverse Drug/Device Reaction

An unexpected ADR is an adverse reaction for which the nature or severity is not consistent with the applicable product information.

8.1.5 Suspected Unexpected Serious Adverse Reaction

An AE suspected to have a causal relationship to an investigational or marketed drug/device and meeting criteria for seriousness and unexpectedness. Suspected unexpected serious adverse reactions (SUSARs) are also reportable for active comparator products, placebo, or the clinical study protocol itself (i.e. events due to study procedures).

8.1.6 Unanticipated Adverse Device Effect

An unanticipated adverse device effect (UADE) means any serious adverse effect on health or safety or any life-threatening problem or death caused by, or associated with, a device, if that effect, problem, or death was not previously identified in nature, severity, or degree of incidence in the investigational plan or application (including a supplementary plan or application), or any other unanticipated serious problem associated with a device that relates to the rights, safety, or welfare of subjects.

8.1.7 Adverse Events Related to Hemodialysis Therapy (Anticipated Adverse Events)

The following are common adverse reactions (signs, symptoms and diagnoses) that have been reported related to HD therapy: hypotension; hypertension; muscle cramps; nausea; vomiting; headache; chest pain; back pain; itching; fever; chills; disequilibrium syndrome; hypersensitivity (allergic) reactions including asthmatic reactions, respiratory arrest, pruritus, urticaria, erythema, and peripheral and facial edema; hypovolemia; hypervolemia; cardiac arrhythmia; cardiac tamponade; intracranial bleeding; seizures; hemolysis; air embolism including micro-air embolism; blood loss; infection; access related problems including infiltration; abdominal pain; fluid overload; hematuria; bleeding; and electrolyte imbalance. Definitions of these adverse reactions are provided in Appendix 1.

8.1.8 Microbiological-Associated Adverse Events

If a failed water sample is accompanied by AEs such as fever, rigors or sepsis within 4 hours after a HD treatment, the event will be considered a microbiological-associated AE(s). The events will be documented on the AE eCRF; the positive culture results will be documented on a Product Issue Form.

A failed dialysate sample from a device actively treating a subject will always be considered a microbiological-associated AE, regardless of whether accompanied by symptoms. The events will be documented on an AE eCRF; the positive culture results will be documented on a Product Issue Form eCRF.

8.1.9 Performing Adverse Events Assessments

The AE collection period for each subject starts with enrollment and completes when the subject ends the study. During the course of the study, the Investigator or designee shall routinely monitor each subject for the occurrence of any AE. Routine monitoring should include regular communication with the trial subject, review of laboratory results, assessment of anticoagulation, dialysis access, medication use, and by reviewing the treatment details in the HemoCare's TM Connectivity Platform as reported by the assigned HemoCare Hemodialysis System. Site team members should follow up and gather additional details from subjects when appropriate based on these information sources as well other data sources including but not limited to physical exams, vital signs, subject questionnaires, and concomitant medication listings.

In addition to AE collection, study sites should discuss the AE reporting process with their study subjects and encourage them to volunteer the applicable information to the appropriate site team members in real time. All site team members should likewise monitor and gather information from subjects if an event is suspected based on subject conversations or data points collected. This level of open dialog should drive the AE collection and reporting process.

During the course of the study, controls will also be in place to consistently solicit AE information during the Weekly Assessments. The site team members will use their clinical judgment to follow up with the subjects and report any applicable event(s).

During these periods the site Investigator or designee is required to contact the subject weekly to discuss their current status, treatment, and condition. These timelines are minimum requirements for the sites to follow, they should follow their local guidelines if more frequent communication is required (e.g., local standard of care or to follow up on current/recent events).

